# 4.10.1.8 Japan specific analysis

A subset of the planned outputs will be repeated for participants from Japan, as required for interaction with the Japanese Regulatory Agency. The outputs will be identified in the tables, listings, and figures (TLF) mock shells.

### 4.10.2 Analysis of exploratory efficacy endpoints

# 4.10.2.1 Percent change from baseline in UACR

UACR will be summarized by treatment group and visit in terms of absolute values, and percentage changes from baseline.

A by-participant listing of the UACR data will be provided. Statistical analyses similar to those described for the primary analysis will be provided.

### 4.10.2.2 NT-proBNP

A summary of the NT-proBNP at baseline and at different visits as well as the percentage change from baseline will be provided by treatment group and time point.

Similar analyses described for the UACR at section 4.10.1.1 and 4.10.2.1 will be conducted for NT-proBNP.

### **4.11 Safety Evaluation**

All safety summaries and analyses will be based upon the SS.

Safety summaries will be presented by treatment group and by eGFR categories ( $<30 \text{ mL/min}/1.73 \text{ m}^2$ ; or  $\ge 30 \text{ to} < 45 \text{ mL/min}/1.73 \text{ m}^2$ ), where appropriate. Individual safety and tolerability data will be provided in data listings.

Where applicable, data will be summarised for the observed value, and for the corresponding change from baseline. Change from baseline will be calculated as the differences between the post-dose value at each time point and the value prior to administration of the study medication.

TP-GDO-WW-016-08 Effective Date: 26 Nov 19 Related to: SOP-GDO-WW-019 CONFIDENTIAL Project Document Version No. 3.0

**Project Document Effective Date**: Date of last signature
Page 25 of 50

### 4.11.1 Extent of Exposure

The duration of exposure (days) will be summarized by treatment group separately for AZD9977 in combination with dapagliflozin and dapagliflozin alone. This will be derived as follows:

 $Duration\ of\ Exposure\ (Days) = Date\ of\ Last\ Dose\ - Date\ of\ First\ Dose\ +\ 1$ 

Treatment duration (days) will be summarized by treatment group for the SS, using descriptive statistics. A by-subject listing of drug administration data will be provided. Dates and times will be listed for each subject and treatment duration.

#### 4.11.2 Adverse Events

All AEs will be recorded from the time of randomisation and SAEs will be recorded from the time of signing the full ICF for the study (Visit 1a). No AE or SAE information will be collected after just signing of the optional pre-screening ICF. Recording of all AEs will continue until the end of the participant's safety follow-up period.

All AEs will be coded using the most recent version of the MedDRA that will have been released for execution at AstraZeneca or designee.

When not otherwise specified only AEs occurring with an onset date, or worsening, on or after first dose of investigational medical product (IMP) and within 28 days after last dose of IMP will be summarized.

The following rules will be used to determine whether or not an AE has taken place on-treatment:

- 1. An AE with an onset date and time on or after the date and time of first dose up to and including 5 days following the date and time of last dose of study treatment will be considered on-treatment
- 2. An AE with an incomplete start date and whose end date is not prior to the time of dosing on Day 1 will be considered to have taken place on-treatment unless the non-missing components of the incomplete start date indicate that the start date falls outside the time from dosing on Day 1 to last dose plus 5 days

The following variables will be collected for each AE:

- Adverse event diagnosis/description (verbatim)
- The date and time when the AE started and stopped
- Maximum intensity
- Whether the AE is serious or not
- Investigator causality rating against the investigational medicinal product AZD9977 and/or the investigational product Dapagliflozin (yes or no)
- Action taken with regard to investigational products (AZD9977 and/or Dapagliflozin)
- Adverse event caused subject's withdrawal from the study (yes or no)
- Outcome

Unless otherwise specified, all summaries will be provided by treatment group for the SS.

The number and percentage of AEs will be presented by SOC and/or PT and for each eGFR category.

In the case that, within a visit, a patient has more than one episode of the same PT with different levels of intensity, action taken, outcome causality or seriousness, then the maximum intensity level, action taken (i.e. withdrawn) and outcome (i.e. fatal), causality level (i.e. related), or seriousness level (i.e. serious), respectively will be used. The following ordering will be used to define maximum intensity level, action taken, outcome causality level, or seriousness level:

- Intensity: Mild < Moderate < Severe

- Causality: No < Yes
- Seriousness: No < Yes
- Action taken: Unknown < Not applicable < Dose not changed < Drug interrupted < Drug withdrawn

- Outcome: Unknown < Recovered/resolved < Recovered/resolved with sequelae < Recovering/resolving < Not recovered/not resolved < Fatal

Summaries of the incidence of AEs will present the number and percentage of participants reporting at least one event in the corresponding AE category. Participants with multiple events in the same AE category will be counted once in that category. Participants with events in more than 1 category will be counted once in each of those categories.

Summaries of the occurrence of AEs will present the number of reported events within the corresponding AE category. Multiple events in the same AE category will be counted multiple times in that category. Multiple events belonging to more than 1 AE category will be counted multiple times in each of those categories.

An overview of AEs will present for each treatment group the number and percentage of patients with

- Any AEs
- Any SAEs
- Any SAE with outcome of death
- Any AEs leading to discontinuation of IMP
- Any AEs leading to withdrawal from study

An additional overview of AEs will be presented for each eGFR category.

The number and percentage of subjects who experience one or more AEs will be tabulated by each treatment group and by:

- SOC and PT
- SOC, PT and baseline eGFR category.
- SOC and PT with outcome of death
- SOC and PT and with discontinuation of investigational product
- SOC and PT and with discontinuation of investigational product by baseline eGFR categories
- SOC and PT and with possibly related adverse events

- SOC and PT and with other action taken
- SOC and PT and seriousness
- Serious AEs by SOC and PT
- Serious AEs by SOC and PT and baseline eGFR categories
- SOC and PT and outcome
- SOC and PT and maximum reported intensity
- SOC and PT and time from first dose to first onset of adverse event (0-21 days, 22-43 days, 44-65 days, 66-85 days, >85 days.
- PT and most common AEs (>5% of participants in any treatment group) Note: This will be sorted by decreasing frequency of PT based on all participant in the SS.
- Number of SAEs by SOC and PT with outcome of death.
- Number of AEs by PT and timing of event i.e., time from first IMP dose to first AE onset (0-21 days, 22-43 days, 44-65 days, 66-85 days, >85 days.).

In addition, a table including the key participant information will be provided for the following:

- Participants reporting SAEs with an outcome of death
- Participants reporting SAEs
- Participants reporting AEs leading to IMP discontinuation

An AE listing for the SS will cover details for each individual AE. A separate AE listing will be provided for participants enrolled but not randomised and participants not exposed to IMP.

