Procedure	Pre- scre enin g	Screeni ng	Start Run-in	Pre- rando- misation	Baseline/ Rando misation			Treatm	ient Pe	riod		EOT/ET a	Safety Follow-u p	Notes	Details in CSP Section or Appendix
Visit ^b	Opti onal	1a	1b	2	3	4	5	6	7	8	9	10	11		-
Week	c	(-8 to -7)* -6 to -5	(-7 to -6)* -5 to -4	-1	1	1	2	3	4	7	10	13	17	* Applies to SGLT2i naïve	For details on run-in period see
Day	c	(-56 to -49)* -42 to -35	(-49 to -42)* -35 to -28	-10 to -3	1	3 ± 1	8 ±2	15 ±3	22 ±3	43 ±3	64 ±3	85 ±3	113 ±4	patients	Section 4.1
Central laboratory serum sample for creatinine for eGFR calculation				X °											Section 8.2.4
Central laboratory serum sample for cystatin C for eGFR calculation				X °	X (pre- dose)	х	х	X	Х	X	Х	х	Х		Section 8.2.4
Central laboratory blood samples for HbA1c, cholesterol, and lipids					X (pre- dose)							X	х	After at least 8-hour fasting for lipids.	Section 8.2.4
Central laboratory urinalysis					X (pre- dose)					Х		Х	х		Section 8.2.4

Procedure	Pre- scre enin g	Screeni ng	Start Run-in	Pre- rando- misation	Baseline/ Rando misation			Treatm	ient Pe	riod		EOT/ET a	Safety Follow-u p	Notes	Details in CSP Section or Appendix
Visit ^b	Opti onal	1a	1b	2	3	4	5	6	7	8	9	10	11		
Week	c	(-8 to -7)* -6 to -5	(-7 to -6)* -5 to -4	-1	1	1	2	3	4	7	10	13	17	* Applies to SGLT2i naïve	For details on run-in period see
Day	c	(-56 to -49)* -42 to -35	(-49 to -42)* -35 to -28	-10 to -3	1	3 ± 1	8 ±2	15 ±3	22 ±3	43 ±3	64 ±3	85 ±3	113 ±4	patients	Section 4.1
Central laboratory urine samples for albumin, creatinine (for UACR calculation), Na ⁺ , K ⁺ , uric acid, urea, osmolality, glucose, and cortisol ^f				X e, f			x		X	X	х	x	X	First morning void urine sample collected at home in provided vials over 3 consecutive days until the visit day.	Sections 8.1.1, 8.5.2, 8.6.1
Pharmaco- kinetics															
Predose sample for AZD9977 and dapagliflozin plasma concentrations							X		x			X		Collected before dose intake at site, or 1 day after last dose for the EOT/ET visit.	Section 8.5.1

Procedure	Pre- scre enin g	Screeni ng	Start Run-in	Pre- rando- misation	Baseline/ Rando misation			Treatn	ient Pe	riod		EOT/ET a	Safety Follow-u p	Notes	Details in CSP Section or Appendix
Visit ^b	Opti onal	1a	1b	2	3	4	5	6	7	8	9	10	11		
Week	c	(-8 to -7)* -6 to -5	(-7 to -6)* -5 to -4	-1	1	1	2	3	4	7	10	13	17	* Applies to SGLT2i naïve	For details on run-in
Day	c	(-56 to -49)* -42 to -35	(-49 to -42)* -35 to -28	-10 to -3	1	3 ± 1	8 ±2	15 ±3	22 ±3	43 ±3	64 ±3	85 ±3	113 ±4	patients	period see Section 4.1

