8.3.1 Time Period and Frequency for Collecting AE and SAE Information

Adverse events will be collected from randomisation (Visit 3) throughout the treatment period and including the follow-up period.

Serious AEs will be recorded from the time of signing of the full ICF for the study (Visit 1a). No AE or SAE information will be collected after just signing of the optional pre-screening ICF.

If the investigator becomes aware of a SAE, with a suspected causal relationship to at least 1 of the IMP, that occurs after the end of the clinical study in a participant treated by him or her, the investigator shall, without undue delay, report the SAE to the sponsor.

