9.4.5.1 Adverse Events

Adverse events will be coded using the most recent version of the MedDRA that will have been released for execution at AstraZeneca or designee.

AEs will be presented for each treatment group by SOC and/or PT covering number and percentage of patients reporting at least 1 event and number of events where appropriate.

Only AEs occurring with an onset date, or worsening, on or after first dose of IMP and within 28 days after last dose of IMP will be presented in summary tables. Serious AEs occurring prior to start of IMP will be included in data listings.

An overview of AEs will present for each treatment group the number and percentage of patients with any AE, AEs with outcome of death, SAEs, and AEs leading to discontinuation of IMP, as well as AEs leading to IMP dose interruptions, and AEs leading to withdrawal from study as well as the number of individual occurrences in those categories.

Separate AE tables will be provided taken into consideration relationship as assessed by the investigator, maximum intensity, seriousness, death, and AEs leading to discontinuation of IMP as well as other action taken related to IMP, other significant AEs, and timing of events.

An additional table will present number and percentage of patients with most common AEs. Most common (eg, frequency of > 5%) will be defined in the SAP.

In accordance with the requirements of the FDA, a separate table will present non-serious AEs occurring in more than 5% of patients in any treatment group.

Key patient information will be presented for patients with AEs with outcome of death, SAEs, and AEs leading to discontinuation of IMP.

An AE listing for the SS will cover details for each individual AE; an AE listing for patients who were not exposed to IMP is presented separately.

Full details of AE analyses will be provided in the SAP.

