#### **Deteriorating renal function monitoring over time**

Absolute value, change and percentage change from baseline in eGFR (central labs) by visit and treatment

SToI analysis of PTs as described in Appendix C: List of preferred termsC: List of preferred terms. This would include an overall summary table of frequencies of AE, SAEs, DAEs, and a summary table by PT based on a pre-defined list of preferred terms

TP-GDO-WW-016-08 **CONFIDENTIAL** Effective Date: 26 Nov 19 **Project Document Effective Date**: Date of last signature Related to: SOP-GDO-WW-019

The summary will be provided for all the AE with an onset date, or worsening, on or after first dose of investigational medical product (IMP) and within 28 days after last dose of IMP and based on the on-treatment definition when otherwise specified. A summary based by eGFR categories will be also presented.

The incidence of hyperkalaemia, hypotension and deteriorating renal function will be summarized by treatment group.

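### The 28-day AE summary window can close before the safety follow-up visit, so an AE whose onset or worsening is dated to that visit may be listed but not tabulated (minor)

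*SAP*

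**What the plan says.** **Collection.** Protocol 8.3.1 collects AEs from randomisation "throughout the treatment period and including the follow-up period". SAP 4.11.2 likewise continues recording to the end of the participant's safety follow-up.

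**Tabulation.** Protocol 9.4.5.1 sets the rule by onset date: "Only AEs occurring with an onset date, or worsening, on or after first dose of IMP and within" 28 days of the last dose. SAP 4.11.2 repeats it as the default for AE summaries: AEs with onset or worsening from first dose "and within 28 days after last dose of IMP will be summarized". In SAP 4.11.3 the same limit governs the preferred-term tables for hypotension and for deteriorating renal function, the latter worded "within 28 days after last dose of IMP and based on the on-treatment definition when otherwise specified". A separate on-treatment definition ends 5 days after last dose.

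**Visit days.** The Schedule of Activities (protocol 1.3) puts Visit 10 (EOT) at Day 85 ±3 and Visit 11 at Day 113 ±4. Its PK sampling note places the sample "1 day after last dose for the EOT/ET visit". A note to the same table says Visit 10 follows completion of 12 weeks of treatment. Protocol 6.7 says participants stop study drug following the EOT visit.

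**Follow-up dapagliflozin.** The footnote to protocol Table 5 classes it as non-investigational in the safety follow-up, so it does not move the date of the last investigational dose.

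**The concern.** The collection period and the summary period end at different points, and neither document gives a reason. Visit 11 includes physical examination, vital signs, central chemistry and haematology, cystatin C and urinalysis, and no visit is scheduled between Visits 10 and 11. Under protocol 8.3.5 a new or aggravated clinically relevant examination finding is reported as an AE. Laboratory or vital-sign deterioration is reported when it meets the criteria given there. An asymptomatic abnormality first seen at Visit 11 may have no earlier evidence of onset and so may be dated to the visit.

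If the window has already closed, such an AE has a listing entry but adds nothing to the between-arm incidence tables, including the preferred-term tables for two of the three safety topics of interest. Whether it is counted then depends on which permitted day the visit took place.

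**Working it through.** **Inputs.** Visit 10 on Day 85 ±3 (Days 82 to 88) and Visit 11 on Day 113 ±4 (Days 109 to 117), from the Schedule of Activities. Window length 28 days, from SAP 4.11.2 and protocol 9.4.5.1. Last dose the day before EOT, from the PK note, with the EOT day itself as an alternative reading of protocol 6.7.

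**The plan's own figure.** Day 85 + 28 = Day 113. The nominal Visit 11 day is reproduced when four weeks are counted from the EOT visit.

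**Nominal window end.** Last dose = 85 − 1 = Day 84, which agrees with 12 × 7 = 84 days of treatment. Window end = 84 + 28 = Day 112. Nominal Visit 11 is 113 − 84 = 29 days after last dose, one day outside. If the last dose is on Day 85, the window ends on 85 + 28 = Day 113 and nominal Visit 11 is just inside.

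**With tolerances.** For each EOT day, count how many of the nine permitted Visit 11 days fall after the window end.

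| EOT day | Window end, last dose EOT − 1 | Visit 11 days outside | Window end, last dose on EOT day | Visit 11 days outside |
|---|---|---|---|---|
| 82 | 109 | 8 | 110 | 7 |
| 83 | 110 | 7 | 111 | 6 |
| 84 | 111 | 6 | 112 | 5 |
| 85 | 112 | 5 | 113 | 4 |
| 86 | 113 | 4 | 114 | 3 |
| 87 | 114 | 3 | 115 | 2 |
| 88 | 115 | 2 | 116 | 1 |
| Total of 7 × 9 = 63 | | 35 (56%) | | 28 (44%) |

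**Spread.** With the last dose the day before EOT, Visit 11 falls between 109 − 87 = 22 and 117 − 81 = 36 days after last dose. With the last dose on the EOT day, the range is 109 − 88 = 21 to 117 − 82 = 35 days.

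**Which events are lost.** On the nominal schedule with last dose on Day 84:
- onset on or before Day 112, first reported at Visit 11: tabulated;
- onset or worsening dated to Visit 11 on Day 113: listed only;
- Visit 11 held on Days 109 to 112: even findings dated to the visit are tabulated.

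**The case against.** A reader might infer that every AE first detected at Visit 11 disappears from every AE table. The documents do not support that. Inclusion turns on the date of onset or worsening, start dates are recorded, and protocol 8.3.4 elicits AEs by asking about health problems since the previous visit. An event that began inside the window and came to light at Visit 11 is counted. Nor does any section state that Visit 11 findings take the visit date as onset. Where a finding accompanies symptoms, protocol 8.3.5 makes the symptom the AE, and its onset may be earlier.

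It would also go too far to say that the follow-up visit's safety information is lost. SAP 4.11.3 counts participants with a residual eGFR decrease above 25% at that visit and summarises serum potassium and eGFR by visit. SAP 4.11.4 and 4.11.6 summarise laboratory and vital-sign data by visit, and SAP 4.11.2 lists every AE in the Safety Set.

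A fixed 28-day limit is also defensible in itself. It matches the stated four-week follow-up after last dose, is the same in both documents and applies to all arms. Running the window to Visit 11 would give late attenders a slightly longer one.

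These arguments limit the size of the point but do not remove it. The fixed limit does not give a common observation period in practice, because Visit 11 may be as early as 22 days after last dose. The default rule allows for exceptions, but no AE table is given a wider window. Reading the last dose as Day 85 brings nominal Visit 11 inside, yet 28 of the 63 day pairs remain outside.

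**Conclusion.** The point holds as a minor misalignment between what is collected and what is tabulated. An AE whose onset or worsening is dated to a Visit 11 held after the window closes is listed but not summarised. On the nominal schedule with last dose on Day 84, the gap is one day. Over the permitted visit days Visit 11 is outside in 35 of 63 pairs, or 28 of 63 if the last dose is on the EOT day.

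These fractions count day pairs for participants who complete treatment. Reading them as probabilities would require all pairs to be equally likely, which is an assumption. They are not shares of AEs or participants, and few events are likely to be affected. That some Visit 11 findings will be dated to the visit is an inference, since the documents give no onset-dating rule. The primary endpoint is untouched.

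**What to change.** In SAP 4.11.2 and 4.11.3 and in protocol 9.4.5.1, define the AE summary window as first dose of IMP through the later of last dose + 28 days and the date of Visit 11. Leave the on-treatment tables (last dose + 5 days) unchanged. The PK note and protocol 6.7 should also be reconciled on when the last dose falls relative to the EOT visit.

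The cost is a wording change in both documents and one derivation, using data already collected. The downside is that a few events up to about 36 days after last dose enter the tables, and the window length varies slightly between participants.

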#### **4.11.3** Safety Topics of Interest

Hyperkalaemia, hypotension and deteriorating renal function are considered safety topics of interest in this study. The analyses below will be done for the overall population as well as each eGFR category ( $<30 \text{ mL/min}/1.73\text{m}^2$ ;  $\ge 30 \text{ to} < 45 \text{mL/min}/1.73\text{m}^2$ ; and  $\ge 45 \text{ mL/min}/1.73\text{m}^2$ ).

#### Hyperkalaemia

Hyperkalaemia will be evaluated by the analysis of serum/plasma  $K^+$  levels (absolute values, change and percentage change from baseline in  $K^+$ , values meeting protocol-mandated discontinuation criteria for hyperkalaemia) and analysis of pre-defined AE preferred terms related to hyperkalaemia.

Hyperkalaemia will be presented as:

# Hyperkalaemia related safety topics of interest

- Number (%) of patients with on-treatment local serum/plasma K+ level > 5.5 mmol/L (confirmed by another local serum/plasma K+ level) \*
- Number (%) of patients with local on-treatment serum/plasma  $K^+$  level > 5.5 mmol/L and central lab serum  $K^+$  >5.5 mmol/L \*\*
- Number (%) of patients with local on-treatment serum/plasma K+ level > 6 mmol/L (confirmed by another local serum/plasma K+ level) \*

- Number (%) of patients with local on-treatment serum/plasma  $K^+$  level > 6 mmol/L and central lab serum  $K^+$  >6 mmol/L \*\*
- Number (%) of patients who met the protocol mandated hyperkalaemia discontinuation criteria in the study:
  - Number (%) of patients with local on-treatment serum/plasma K+ level > 5.5 to ≤ 6 mmol/L confirmed by another local or central serum/plasma K+ level > 6.0 mml/L\*
  - Number (%) of patients with local on treatment serum/plasma K+ level > 6.0 mmol/L confirmed by another local or central serum/plasma K+ level > 6.0 mmol/L\*
- Number (%) of patients who discontinued due to meeting the protocol mandated hyperkalaemia discontinuation criteria in the study†

\*Confirmation has to be the next consecutive lab sample which is  $\leq 7$  days of the original lab sample. If time is available, 7 days is 168 hours from date and time of original lab. If time is missing, then 7 days is study day of original lab sample plus 7.

Additional analysis will include K+ lab values confirmed at the next consecutive lab sample regardless of time from initial lab sample.

\*\*Local and central lab to be on same day.

†Based on the end of treatment CRF page

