Appendix F Management of Hyperkalaemia and Deteriorating Renal Function

F 1 Hyperkalaemia

At all baseline and on-treatment visits (according to the SoA) K^+ will be measured in either serum or plasma samples at a local laboratory depending on the laboratory's capability and in serum samples at a central laboratory. Repeat samples should be sent for both central and local laboratory assessment.

Inappropriate sample handling/storage or lengthy transport time to the central laboratory may result in falsely elevated serum K^+ levels in the centrally analysed blood samples. It is expected that local laboratory results (from either serum/plasma samples) will be available prior to central laboratory results and expected to take priority for decision-making/monitoring:

- Serum/plasma $K^+ > 5.5$ to $\leq 6 \text{ mmol/L}$ (based on local laboratory samples) should be reassessed within 72 hours.
 - If the repeat local laboratory sample has serum/plasma $K^+ > 6.0$ mmol/L, study treatments must be discontinued permanently.
 - If the repeat local laboratory sample has serum/plasma $K^+ > 5.5$ to ≤ 6.0 mmol/L, consider corrective actions, including dietary changes and/or adjustment/discontinuation of non-essential medications that might have caused or contributed to hyperkalaemia and reassess within 72 hours:
 - If local serum/plasma K⁺ remains > 5.5 mmol/L to ≤ 6 mmol/L, consider permanent discontinuation or continue monitoring at the discretion of the investigator. Permanently discontinue if repeat local and/or central samples have serum/plasma K⁺ > 6.0 mmol/L.
- Serum/plasma K⁺ > 6 mmol/L (based on local laboratory samples) should be reassessed immediately and study treatments should be discontinued temporarily while waiting for results:
 - If the repeat local laboratory sample has serum/plasma $K^+ > 6.0 \text{ mmol/L}$, study treatments must be discontinued permanently.
 - If the repeat local laboratory sample has serum/plasma $K^+ > 5.5$ to ≤ 6.0 mmol/L and the central laboratory sample has serum K^+ is > 6.0 mmol/L, study treatments must be discontinued permanently.
 - If the repeat local laboratory sample has serum/plasma $K^+ > 5.5$ to ≤ 6.0 mmol/L and the central laboratory sample has serum $K^+ \le 6.0$ mmol/L, based on the discretion of the Investigator, consider corrective actions, including dietary changes and/or adjustment/discontinuation of non-essential medications that might have caused or

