contributed to hyperkalaemia; and/or continuation with reassessment; or permanent discontinuation.

- If the repeat local laboratory sample has serum/plasma $K^+ \le 5.5 \text{ mmol/L}$, then study treatments can be resumed, even if the central laboratory sample has serum $K^+ > 6.0 \text{ mmol/L}$.

If the investigator is aware of any change in the participant's clinical status that may influence serum electrolyte levels or fluid balance (eg, vomiting and/or diarrhoea > 1 day), it is recommended to reassess serum/plasma K^+ levels as soon as possible after the acute event. In case of permanent discontinuation, serum/plasma K^+ levels should be monitored until resolution or stabilisation.

F 2 Deterioration of Renal Function

Serum creatinine will be measured both at a local laboratory and a central laboratory at all baseline and on-treatment visits according to the SoA. Repeat samples should be sent for both central and local laboratory assessment. It is expected that local laboratory results will be available prior to central laboratory results. As local and central laboratories will calculate eGFR using different formulas, central eGFR values should always be compared to central eGFR values and local eGFR values should always be compared to local eGFR values. For local laboratories, the eGFR assessment at Visit 3 (prior to the start of study treatment) will be taken as the baseline eGFR value.

- If eGFR shows a 30-50% decline from baseline and an absolute value ≥ 15 mL/min/1.73 m² (based on local and/or central laboratory samples), eGFR should be reassessed within 1 week.
 - If persistent 30-50% decline stabilises upon weekly follow-ups, eGFR monitoring may return to the standard SoA, at investigator's discretion.
- If eGFR shows a >50% decline from baseline and/or decreases to an absolute value < 15 ml/min/1.73 m² (based on local and/or central laboratory samples), eGFR should be reassessed within 48 hours.
 - If eGFR shows a 30% to 50% decline from baseline and an absolute value $\geq 15 \text{ mL/min/1.73 m}^2$, eGFR should be reassessed within 1 week.
 - If eGFR again shows a >50% reduction from baseline and/or absolute value
 <15 mL/min/1.73 m², study treatments must be discontinued immediately and eGFR should be followed up within a week and weekly until signs of improvement and stabilisation.

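### One SAP sub-row on meeting the mandatory hyperkalaemia stop counts patients whom Appendix F 1 allows to resume treatment

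*SAP*

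**What the plan says.** **SAP, Hyperkalaemia related safety topics of interest.** One row counts patients who met the protocol-mandated hyperkalaemia discontinuation criteria. It has two sub-rows, split by the first local K+: above 5.5 and up to 6 mmol/L, or above 6.0 mmol/L. In both, the patient counts if that value is "confirmed by another local or central serum/plasma" K+ above 6.0. The footnote to both reads "Confirmation has to be the next consecutive lab sample which is" no more than 7 days after the first sample. A further analysis lifts the time limit and takes "lab values confirmed at the next consecutive lab sample regardless of time from initial lab sample". Neither version puts a condition on the repeat local value.

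**Protocol Section 7.1.** Treatment must stop for K+ above 6.0 in two consecutive samples, or for K+ above 5.5 with a repeat above 6. No laboratory is named. The same bullet refers to Appendix F 1 for details.

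**Protocol Appendix F 1.** Repeat samples go to both laboratories. The appendix warns: "Inappropriate sample handling/storage or lengthy transport time to the central laboratory may result in falsely elevated serum" K+. Local results are therefore "expected to take priority for decision-making/monitoring". After a first local K+ above 6.0:

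- Repeat local above 6.0: treatment must stop.
- Repeat local above 5.5 and up to 6.0, where the central value "is > 6.0 mmol/L, study treatments must be discontinued permanently".
- The same repeat local with central at or below 6.0: investigator's discretion.
- Repeat local at or below 5.5: "then study treatments can be resumed, even if the central laboratory sample has serum" K+ is above 6.0.

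**The concern.** The row's label says that it counts a mandatory stop. In the branch that starts with a local value above 6.0, the SAP keeps Appendix F 1's central-confirmation route but drops the condition attached to it. The pattern this lets in is a reassuring repeat local with a high central value. Appendix F 1 foresees that pattern and exempts it, because central K+ can be falsely high.

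Hyperkalaemia is a named safety topic of interest. The same list has a row, taken from the end-of-treatment CRF page, for patients who actually discontinued for meeting these criteria. A patient who properly resumed would be in the first row and not in the second, and could be mistaken for a case where the site failed to apply a mandatory stop.

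**Working it through.** There is no stated figure to reproduce. The check sets the SAP rule beside Appendix F 1 for every pattern of results.

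**Inputs.** The first local value is above 6.0 mmol/L (second sub-row). The repeat local value has three bands: at or below 5.5, above 5.5 and up to 6.0, above 6.0. The central value at the repeat draw has two: at or below 6.0, above 6.0. That gives 3 × 2 = 6 patterns.

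**SAP rule, read at the next draw:** count if the repeat local is above 6.0 or the central is above 6.0.

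**Appendix F 1 rule:** stop if the repeat local is above 6.0, or if the repeat local is above 5.5 and up to 6.0 and the central is above 6.0.

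| Repeat local | Central | Appendix F 1 | SAP counts? |
|---|---|---|---|
| ≤ 5.5 | ≤ 6.0 | may resume | no |
| ≤ 5.5 | > 6.0 | may resume | **yes** |
| > 5.5 to ≤ 6.0 | ≤ 6.0 | discretion | no |
| > 5.5 to ≤ 6.0 | > 6.0 | must stop | yes |
| > 6.0 | ≤ 6.0 | must stop | yes |
| > 6.0 | > 6.0 | must stop | yes |

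The SAP counts 1 + 1 + 2 = 4 patterns and Appendix F 1 mandates a stop in 1 + 2 = 3. The difference is 4 − 3 = 1, the second line. No mandatory stop is missed. Adding the condition on the repeat local removes that line, and all six then agree.

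**First sub-row (first local above 5.5 and up to 6.0), same six patterns.** The SAP again counts 4. A repeat local above 6.0 is a mandatory stop (2 patterns). Once the value persists above 5.5 and up to 6.0, Appendix F 1 says "Permanently discontinue if repeat local and/or central samples have serum/plasma" K+ above 6.0, which supports a third. The remaining counted pattern is a repeat local at or below 5.5 with central above 6.0. Appendix F 1 does not address it in this branch, and Section 7.1's clause on a repeat above 6, with no laboratory named, can cover it. That is silence, not contradiction.

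**Scale.** The patterns are logical cells, not frequencies. As an illustration, one misclassified patient in an arm of 125 moves that arm's percentage by 1/125 = 0.8 points. The analyses are repeated by eGFR category. If the lowest category held the planned minimum of 20% of 500 = 100 patients, or 100/4 = 25 per arm, one patient would move its percentage by 1/25 = 4 points.

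**The case against.** The best defence is that the two sub-rows follow Section 7.1 closely. Section 7.1 asks for two consecutive samples above 6.0 from any laboratory, and it cites Appendix F 1 for monitoring and management. The tension is then partly inside the protocol, and Appendix F 1's wording on resuming is permissive: it does not say that the criterion was not met. This stands in part. But Appendix F 1 is the only place that settles split local and central results, and Section 7.1 points to it. A pattern in which treatment may resume cannot fairly carry a label that says the stop was mandated.

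A second objection is that Appendix F 1 does not say which draw supplies the central value. This also stands, and the fix has to deal with it. It does not rescue the sub-row: with a repeat local at or below 5.5, neither mandatory clause in this branch applies, whichever draw is meant.

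A third is that the consequence is small. Neighbouring rows give local-only confirmation, same-day local and central agreement, and actual discontinuations, and the error can only over-count. That is correct, and it limits the weight of the point.

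A reader might go further and infer that the central sample from the same draw could serve as the next consecutive sample, so that some mandatory stops are missed. The SAP does not support this. It uses one footnote for rows that pair local and central values on the same day and a different one for confirmation by the next sample. The rows at issue carry the second.

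**Conclusion.** The point holds for the second sub-row and for its version without the time limit. Read at the next draw, that sub-row counts one pattern (first local above 6.0, repeat local at or below 5.5, central above 6.0) in which Appendix F 1 lets treatment resume. The effect is a possible over-count in one descriptive safety row. Severity is minor: no hypothesis test and no dosing decision depends on it.

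The finding that no mandatory stop is missed assumes that Appendix F 1's central value comes from the repeat draw. The number of patients affected depends on how often the laboratories disagree in this way, and the documents do not give that.

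A reader might also infer that the first sub-row is wrong. It should not be narrowed: Appendix F 1 is silent on its only doubtful pattern, and Section 7.1 can be read to include it. Nor does anything here suggest that stopping decisions at sites are affected, since sites follow the protocol and not the SAP table.

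**What to change.** Amend the SAP only, before unblinding. In the second sub-row, and in its version without the time limit:

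- Count a repeat local K+ above 6.0 mmol/L.
- Count a central K+ above 6.0 only when the repeat local is above 5.5 and up to 6.0.
- Do not count when the repeat local is at or below 5.5, whatever the central value.
- State which draw supplies the central value.

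Leave the first sub-row, the other hyperkalaemia rows and Section 7.1 unchanged. The cost is one programming condition and a sentence in a new SAP version, which the SAP Introduction already provides for when changes come before database lock. No protocol amendment and no new data are needed.
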